12.8 Safety Variable Analyses

All ITT subjects will be evaluable for safety. The number and percent of subjects reporting AEs (including treatment-emergent laboratory abnormalities) will be tabulated by randomized treatment group. All serious AEs (SAEs) will be tabulated separately as well as included with all reported AEs.

Physical and neurologic assessments, laboratory results, vital signs (including orthostatic measurements), ECGs, and C-SSRS will be summarized using descriptive statistics.

12.9 Pharmacokinetic Analysis

Individual plasma concentrations of YKP3089 will be tabulated with the corresponding time related to study drug administration by dose group.

Descriptive statistical analyses will be performed on the plasma concentrations of the YKP3089 obtained during steady-state treatment (Visit 7 and 8)

Descriptive statistical analyses will be performed on the plasma concentrations of the concomitant AEDs obtained during steady-state concomitant treatment (Visit 7 and 8) and those at baseline (Visit 3) to assess the effect of YKP3089 on these AEDs.

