- e. Administer the Baseline/Screening version of the C-SSRS at Screening. Administer the Since Last Visit version at all subsequent visits.
- f. 12-lead ECG will be performed 3 times with a minimum of 2 minutes between recordings.
- g. For female subjects of childbearing potential: If pregnancy is suspected at any time during the study, an interim test may be performed.
- h. Laboratory Assessment: Safety assessment includes blood chemistry and hematology. If the subject meets an exclusion criterion at Visit 1, an unscheduled laboratory sampling can be repeated for confirmation. Local laboratories may be used if necessary.
- i. Two blood samples will be collected for the determination of YKP3089 plasma levels: the first one will be collected upon subjects' arrival to the study unit; the second one should be collected within 2 to 4 hours after the first blood draw.
- j. Trough levels of concomitant AEDs should be obtained whenever possible. If this is not feasible due to the time of the clinic visit, appointments should be made so that the time of the blood draws are consistent with the last dose of concomitant AEDs throughout the study.
- k. If a CT or MRI has not been performed within the last 10 years, one must be performed prior to randomization. If an EEG report cannot be obtained, and the subject is otherwise eligible, an EEG may be performed
- l. Seizures occurring on Day 1 will not be counted in the study. Day 1 values will be used as safety baseline. Dosing will commence on Day 2.
- m. Subjects will be contacted by phone on Days 8, 22 and 36 to assess tolerability and the occurrence of any early treatment-emergent adverse events and to reinforce compliance
- n. The investigator will complete the questionnaire at Visit 9 (end of maintenance or early termination if applicable)
- o. The subject will complete the questionnaire at Visit 3 and Visit 9 (end of maintenance or early termination if applicable). This questionnaire is only to be implemented in the countries where it is available and validated for the spoken language(s).

Table 2. Study Assessment Flow Chart for Open-Label Extension Phase

Visit windows of ± 3 days allowed for Visits 9 and Visit 17 (end of study follow-up visit) Visit windows of ± 2 days allowed for Visits 11 and 12. Visit windows of ± 7 days allowed for all other open-label visits	Treatment								End of Study Follow-up

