Preclinical and clinical studies have shown that YKP3089 is well absorbed after oral administration under fasting and fed conditions. A single ascending dose study showed that the half-life of YKP3089 in human subjects was 50.2 ± 15.0 hours (mean \pm SD) for a 100-mg oral dose, 54.7 ± 16.1 hours for a 200-mg oral dose, and 60.4 ± 11.2 hours for a 300-mg oral dose. These values suggest that YKP3089 is suitable for once-daily oral dosage. Details of these preclinical and clinical studies can be found in the current version of the Investigator's Brochure.

Protein binding in human plasma was concentration-independent at the range of 0.114 to 1.4 µg/mL. The protein-bound fraction in human plasma was 61%, with 39% free fraction. [¹⁴C] YKP3089 was preferentially bound to human albumin protein (~66.7%) and not to α₁-acid glycoprotein.

A bioavailability study showed that YKP3089 undergoes minimal first-pass metabolism in humans. Preclinical studies showed that YKP3089 did not produce any strong inhibitions or inductions of cytochrome P450 (CYP) isozymes, UDP-dependent glucuronosyltransferase, or phenol sulfate transferase. Studies of the metabolism of YKP3089 showed several possible metabolic pathways. However, only the parent compound and the metabolite produced by glucuronidation of the carbamate nitrogen were recovered in human plasma. This suggests limited potential for metabolite toxicity.

A mass balance study in human subjects indicated limited penetration of YKP3089 and its metabolites into cellular elements of blood. More than 50% of the radioactivity from a radiolabeled dose of YKP3089 was excreted in urine and feces within 24 hours; 93% was excreted within 312 hours. For more information, see the Investigator's Brochure.

Clinical studies of drug-drug interactions showed that YKP3089 had no pharmacokinetic interaction with divalproex. Co-administration of YKP3089 did produce a 19% decrease in exposure to carbamazepine (CBZ) plus CBZ epoxide; however, this decrease was not considered clinically relevant. Co-administration of YKP3089 with an oral contraceptive (1 mg norethindrone and 0.035 mg ethinyl estradiol) showed that the contraceptive had no effect on the pharmacokinetics of YKP3089; however, the YKP3089 apparently increased the area under the concentration-time curve from 0 to 24 hours postdose (AUC₀₋₂₄) for norethindrone by 37%. Details of the drug-drug interaction studies can be found in the current version of the Investigator's Brochure.

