Thereafter, the subjects may at the discretion of the investigator, recommence the upward titration at 50-mg increments in the daily dose once a week towards the target dose until week 6. If the subject cannot tolerate the new upward titration, the daily dose can be reduced one time by 50 mg through the end of week 8. No upward titration will be allowed after Week 6. No two consecutive dose reductions will be allowed.

If a tolerability issue occurs, dosage adjustments need to be made at a scheduled visit or at an unscheduled visit at the discretion of the investigator. At the visit, the subject will be issued a new set of cards to be determined by the interactive web response system (IWRS).

To improve tolerability, the investigator may instruct the subject to take the dose of study medication in the evening. The investigator may alter the timing or amount of an individual dose of a concomitant AED, but the total daily dose and dosing frequency of the concomitant AED must remain unchanged during the double-blind phase.

During titration, the investigator may instruct the subject to hold the daily dose of the study drug up to a maximum of 2 days per week.

6.1.2.2 *Double-Blind Maintenance Phase*

After the 6-week up-titration phase, subjects will enter the double-blind maintenance phase. The subjects will be instructed to take their study medication once daily in the morning for 12 weeks. Subjects will follow the schedule of study visits and assessments detailed in [Table 1](#).

The investigator may instruct the subject to take the dose of study medication in the evening if clinically indicated and consistent with other aspects of the protocol. The investigator may alter the timing or amount of an individual dose of a concomitant AED, but the total daily dose and dosing frequency of the concomitant AED must remain unchanged during the double-blind phase. No YKP3089 dose adjustments are permitted after week 8.

6.1.2.3 *Blinded Study Drug Taper: Termination at End of Double-Blind Phase*

Subjects who will not participate in the optional open-label phase will enter a 3-week, double-blind taper period when they complete the maintenance phase or discontinue prematurely. The dosage of YKP3089 will be tapered according to the schedule shown in [Table 4](#). To maintain

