The investigator will complete the CGIC questionnaire at Visit 9 (end of maintenance or Early Termination if applicable) to assess the subject's clinical status since starting study drug. This assessment should take into account seizure frequency and severity, the occurrence of AEs, and overall functional status of the subject ([Appendix G: Clinical Global Impression of Change \(CGIC\)](#)).

6.2.6.2 *Quality of Life in Epilepsy Questionnaire (QOLIE-31-P)*

Subjects will complete the QOLIE-31-P at Visit 3 (end of baseline) and Visit 9 (end of maintenance or Early Termination if applicable) to assess their status since starting study drug. Note, the QOLIE-31-P will only be completed by the subject; the caregiver will not be allowed to complete this questionnaire on behalf of the subject ([Appendix H: Quality of Life in Epilepsy \(QOLIE-31-P\)](#))

QOLIE-31-P *must* be completed as described in [Appendix H: Quality of Life in Epilepsy \(QOLIE-31-P\)](#). Subjects *must not* have had any simple motor or complex partial seizures within 4 hours, or generalized seizures within 24 hours before administration of the scale. If subjects have these seizure types but have fully recovered from their seizures, the outcome scale may be administered to the subjects. If subjects have not fully recovered from their seizures, the outcome scale only will be done at an unscheduled visit after recovery from seizures. If subjects experience daily seizures and the visit cannot be rescheduled, the outcome scale will be omitted. If a subject is cognitively impaired and unable to understand the scale or if a subject is unable to read, the subject will be excluded from the completion of the scale.

This questionnaire is only to be implemented in the countries where it is available and validated for the spoken language(s).

6.2.7 *Pharmacokinetic Endpoints*

Trough AED levels (oxcarbazepine [OXC], topiramate [TPM], carbamazepine [CBZ], valproate [VPA], lamotrigine [LTG], lacosamide (LMD) and levetiracetam (LEV) only) during the baseline will be compared to those during the treatment period in subjects randomized to 100, 200, or 400 mg/day YKP3089 or placebo to determine potential drug interactions.

6.3 **Safety Assessments**

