12.2 Statistical Methods

Summary statistics and analyses will be presented by the treatment group category assigned to the subject regardless of the dosage of drug administered. Categorical variables will be summarized as frequencies and percentages. Descriptive statistics for continuous variables will include sample size, mean, median, standard deviation, and minimum and maximum values. SAS[®] version 9.2 or later will be used for all data summaries, statistical analyses, and data

listings. Inferential statistical tests will be 2-sided and will employ a tolerance for type I error (alpha, α) of 0.05. Data will be used as collected. Full details of the analysis plan will be included in the Statistical Analysis Plan (SAP) and finalized prior to any un-blinding of efficacy data.

Analyses of Missing Data

The primary efficacy endpoint definition in the United States and Rest of the world states that seizure rates will be calculated using days with non-missing seizure data. The definition does not explicitly account for days with missing data, i.e., days during which the presence or absence of seizures was not recorded in personal diaries. However the definition implicitly accounts for missing data in that it is identical to a definition in which days with missing data are assumed to have the same seizure rate as days with non-missing data.

Similar to the United States definition of the primary efficacy endpoint, the primary endpoint (responder) definition in the countries of Europe, Australia, New Zealand and South Africa implicitly accounts for missing data during maintenance phase in that it is identical to a definition in which days with missing data are assumed to have the same seizure rate as days with non-missing data. An additional analysis will be performed in which subjects who dropped out during the titration phase will be included in the analysis by having their maintenance phase data imputed using the available titration data.

The same approach will be used for missing data in the analysis of all secondary efficacy endpoints.

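### Section 12.9 only describes AED concentrations by group; using each subject's own baseline, a placebo contrast and the recorded AED dose times would make the comparison promised in 6.2.7 much more precise

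*Protocol*

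**What the plan says.** Protocol section 6.2.7 defines the pharmacokinetic endpoint. Trough levels of seven named AEDs "during the baseline will be compared to those during the treatment period in subjects randomized to 100, 200, or 400 mg/day YKP3089 or placebo", with the aim of finding potential interactions.

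Section 12.9 gives the analysis: "Descriptive statistical analyses will be performed on the plasma concentrations of the concomitant AEDs obtained during steady-state concomitant treatment (Visit 7 and 8") and on the Visit 3 levels, "to assess the effect of YKP3089 on these AEDs". Nothing further is specified for AEDs. Section 12.2 adds two things. The descriptive statistics for continuous variables are sample size, mean, median, standard deviation, minimum and maximum. The grouping is also fixed: "Summary statistics and analyses will be presented by the treatment group category assigned to the subject regardless of the dosage of drug administered".

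Timing is dealt with at collection. Table 1, footnote j, says "Trough levels of concomitant AEDs should be obtained whenever possible"; failing that, "appointments should be made so that the time of the blood draws are consistent with the last dose of concomitant AEDs throughout the study". Section 9.5 puts the time of each draw and the preceding AED dosing record on the CRF. Section 6.1.2.1 permits some change after baseline: "The investigator may alter the timing or amount of an individual dose of a concomitant AED", although total daily dose and dosing frequency must not change.

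Section 4.4.2 supplies the only interaction size relevant here: "Co-administration of YKP3089 did produce a 19% decrease in exposure to carbamazepine (CBZ) plus CBZ epoxide". The same sentence says the decrease was not considered clinically relevant.

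The supplied SAP covers only the open-label extension and contains no AED-level analysis. It mentions a separate double-blind SAP, which is not in the file.

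**The concern.** The endpoint is a comparison, but the method stops at describing concentrations at each time. Three things the design already provides are not used.

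- **The subject's own baseline.** AED levels can be expected to differ widely between people because prescribed doses differ. A ratio to the subject's own Visit 3 level removes that spread, and the fixed total daily dose makes the ratio interpretable. Group means at two times do not remove it. Subjects who leave before Visit 7 also contribute to the baseline summary but not to the treatment summary.
- **The placebo group.** It is shown alongside, but no active-versus-placebo contrast or interval is named.
- **The recorded AED dose times.** No analysis uses them.

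Other parts of the protocol are more specific. Section 12.9 tabulates YKP3089 levels with time relative to dosing. Section 12.7, also descriptive, specifies change from baseline and the difference from placebo for QOLIE-31. The AED endpoint has none of these. At stake is whether the trial can say anything useful about a modest change in a background AED.

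**Working it through.** **The plan's own figure.** Section 12.1 states 100 per group for 80% power on the seizure endpoint (difference 16, SD 40, two-sided 0.05). This reproduces: n = 99 per group, and power 80.7% at 100. It says nothing about AED levels, for which the documents give no sample size, variability or user count. All inputs below are therefore assumptions.

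**Illustration 1: arm against placebo.** Assume 20 users of one AED per arm, between-subject SD of log concentration sb = 0.5 to 0.7, and within-subject SD sw = 0.2 to 0.3. The CI factor is exp(1.96 × SE).

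| Comparison | SE formula | SE | 95% CI factor |
|---|---|---|---|
| Raw level, one visit | √(sb² + sw²) × √(2/20) | 0.170 to 0.241 | 1.40 to 1.60 |
| Raw level, mean of Visits 7 and 8 | √(sb² + sw²/2) × √(2/20) | 0.164 to 0.231 | 1.38 to 1.57 |
| Within-subject ratio, mean of Visits 7 and 8 over Visit 3 | √(sw² + sw²/2) × √(2/20) | 0.077 to 0.116 | 1.16 to 1.26 |

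The second row puts the raw and paired comparisons on the same two visits; averaging helps the raw comparison very little. For a 90% interval the multiplier is 1.645, and the paired factor becomes exp(1.645 × 0.077) = 1.14 to exp(1.645 × 0.116) = 1.21.

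As a size benchmark, a 19% fall is a ratio of 0.81, and 1/0.81 = 1.23. Raw levels do not resolve that anywhere in the assumed range. The paired 95% factor does over most of it, but not at the noisiest end (1.26).

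**Illustration 2: a second set of assumptions.** Take 10 to 40 users per arm, between-subject CV 40% to 60%, within-subject CV 20% to 30%, a true ratio of 0.81, two-sided 0.05, and a single on-treatment value. With m users and log-scale SDs:

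- Visit 7-8 against Visit 3 in one arm, treated as unpaired: SE = √(2(sb² + sw²)/m); power 11% to 59%.
- Within-subject ratio in one arm: SE = sw√(2/m); power 36% to over 99%.
- Within-subject ratio against placebo: SE = 2sw/√m; power 20% to 92%.

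At m = 20 with CVs of 40% and 20%, the 95% interval around 0.81 is 0.62 to 1.06, 0.72 to 0.92 and 0.68 to 0.96 respectively.

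The unpaired formula is what a reader must use when given only means and SDs at each time, because those summaries carry no within-subject correlation.

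**Timing.** A draw later by ln(1/0.81)/ln 2 = 0.304 half-lives lowers that sample by 19%. For assumed half-lives of 6, 12 and 24 h this is 1.8, 3.6 and 7.3 h. This is a shift in one subject, not in a group. If 20% of users (assumed) were drawn 3 h late with a half-life of 8 h, each would fall to 2^(−3/8) = 0.77, and the group geometric mean to 0.77^0.2 = 0.95.

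**The case against.** **Grouping and placebo.** A reader might infer that AED levels are pooled over dose groups or that placebo is left out. Sections 12.2 and 6.2.7 rule out both: summaries are by assigned group and placebo is in the set. What is missing is a stated contrast.

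**Timing.** A reader might infer that AED timing is unchecked. Footnote j and section 9.5 control and record it. Only its use in the analysis is unspecified, and the documents do not say how often AED dose times will change or whether this will differ by arm. If footnote j is followed, late draws should be uncommon, and the group-level effect above is small. Timing is secondary to pairing.

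**The 19% figure.** It is exposure to carbamazepine plus its epoxide in a separate study, not a trough change, and the protocol calls it not clinically relevant. It serves here only as a yardstick.

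**Confounding.** A reader might conclude that an undetected AED change would confound the seizure and adverse-event comparisons. It would not. A change caused by randomized YKP3089 is part of the effect of adding the drug; only the attribution of mechanism is affected.

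**Recoverability.** On the same subjects, the ratio of geometric means at two visits equals the geometric mean of the within-subject ratios, so the estimate is not wholly lost. But section 12.2 lists ordinary means and SDs, the subjects at Visit 3 and Visits 7-8 need not be the same, and the paired interval cannot be rebuilt from such tables.

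**Status of the endpoint.** AED interaction is not among the study objectives, no decision is stated to depend on it, and section 12.2 leaves full detail to a SAP. The relevant SAP is unseen. These points stand, and they limit the weight of the finding.

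**Conclusion.** The gap in section 12.9 is real and modest. As written, the analysis does not use the subject's own baseline, a placebo contrast or the recorded AED dose times, so it delivers the comparison promised in 6.2.7 with much less precision than the collected data allow. On the assumed inputs, pairing narrows the 95% CI factor against placebo from 1.40 to 1.60 down to 1.16 to 1.26. User counts and both variance components are assumptions, and at the noisiest end even the paired analysis would not resolve a ratio of 0.81 at 95%. The documents do not show that an interaction will be missed or falsely produced. Whether the double-blind SAP already closes the gap cannot be determined from the file. This is a cheap improvement.

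**What to change.** In section 12.9, for each AED and dose group, among subjects with both samples, report the geometric mean of the within-subject ratio of the Visit 7-8 level to the Visit 3 level with a 90% confidence interval, and that ratio relative to placebo with its interval. State how many subjects lack a pair.

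Use all pairs in the main analysis. As a sensitivity analysis, show the pairs with an unchanged AED dose split and a similar recorded time since the last AED dose, with the tolerance fixed in advance. State that this subset is selected after randomization and may differ by arm, which is why it should not be the main analysis.

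If the double-blind SAP already specifies this, cross-reference it from 12.9 instead.

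The cost is plan wording and a little extra analysis. No new samples or visits are needed, since the levels and times are already collected. The small downside is that only subjects with both samples contribute.

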12.10 Open-Label Extension Analyses

The results of the open-label extension will be reported at a later date using summary tables, figures, and data listings.

12.11 Interim Analysis

No interim analysis will be performed

13 LEGAL ASPECTS, ETHICAL AND ADMINISTRATIVE ISSUES

13.1 Good Clinical Practice

This study is to be conducted according to US and international standards of GCP (FDA Title 21 parts 50 and 312 and ICH guidelines), applicable government regulations, and institutional research policies and procedures. This protocol and any amendments will be submitted to a properly constituted independent EC/IRB, in agreement with local legal prescriptions, for formal approval of the study conduct. The decision of the EC/IRB concerning the conduct of the study will be made in writing to the investigator and a copy of this decision will be provided to the Sponsor before commencement of this study. The investigator should provide a list of EC/IRB members and their affiliate to the Sponsor.

13.2 Documentation of Consent

Written consent of a subject, using the EC/IRB-approved consent form, will be obtained before that subject undergoes any study procedure. The individual who consents the subject must be listed on the delegation log and be authorized to obtain consent. All subjects will have adequate time to ask questions and will be provided with a signed copy of the consent for his/her records. The consenting process will be clearly documented in the subject's chart. The principal investigator is responsible for ensuring that valid consent is obtained and documented for all subjects.

13.3 Delegation of Investigator Responsibilities

The qualified investigator will ensure that all persons assisting the trial are adequately qualified, informed about the protocol, any amendments to the protocol, the study treatments, and their trial-related duties and functions. The qualified investigator will maintain a list of sub-investigators and other appropriately qualified persons to whom he delegates significant trial-related duties.

